#### 10.4. Pharmacokinetic Statistical Analyses – Dose Proportionality (Power Model)

A non-linear Power Model will be used to assess dose-proportionality for baseline adjusted GCaSe Activity Levels in Part 1 of the study in all matrices (plasma, leukocytes, DBS). Actual dose received by each patient will be used. The proportional relationship between the expected value of each parameter  $E(y)$  and dose is written as a power function:

$$E(y) = \alpha * \text{dose}^{\beta} \text{ [Equation 1]}$$

where ' $\alpha$ ' is a constant, ' $\beta$ ' is the proportionality constant and ' $y$ ' is the parameter of interest. The exponent,  $\beta$ , will be estimated by performing a linear regression of  $\ln(\text{parameter})$  [ $C_{\max}$  and  $AUC_{\text{last}}$ ] versus  $\ln(\text{dose})$ . The exponent,  $\beta$ , is the estimated slope of the resulting regression line, since taking logs of Equation 1 gives the linear relationship:

$$\ln(y) = \alpha + \beta * \ln(\text{dose}) \text{ [Equation 2]}$$

The relationship is dose proportional when  $\beta = 1$ .

Linear regression plots of systemic exposure ( $C_{\max}$  and  $AUC_{\text{last}}$ ) versus dose will be presented using log-log scales with the power model overlaid.

#### 11. Shedding

Clearance of vg in plasma, saliva, urine, stool, and semen will be summarized by study part, dose cohort, and overall. Viral shedding data will be presented in a listing.

#### 12. GCaSe Immune Response

Immune response to the GCaSe transgene product measured as change from baseline to each assessment point in total anti-GCaSe antibody titer and neutralizing antibody titer will be summarized (the number of participants with non-missing data, median, min, max, geometric mean, geometric coefficient variation) separately by study part, dose cohort, and overall. Summary table will also include total and neutralizing titer assessments (screening cut point, screening response, specificity, titer), where applicable.

GCaSe immune response data will be presented in a data listing.

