In Gaucher disease, the presence of anti-GCase antibodies is not generally considered clinically significant and there is no correlation with safety and efficacy in prior Gaucher disease type 1 development programmes [[Pastores 2016](#)]. The development of de novo anti-human GCase neutralising antibodies would be unexpected in liver directed AAV gene therapy since such liver directed therapy is reported to be immune tolerising for liver expressed and secreted protein. More than 100 patients with haemophilia B have been given gene therapy to date across multiple studies and no inhibitors have been reported [[Arruda 2016](#)]. Therefore, the risk of developing antibodies, with subsequent loss of efficacy from rescue ERT, is thought to be very low, and similar in both previously treated and treatment naïve patients.

Risk of Infusion-related Toxicity

Allergic-type reactions, including anaphylaxis are a rare consequence of administration of biologics. Onset of anaphylaxis is usually rapid following injection of an allergen with 90% beginning within 40 minutes. Patients with a known or suspected intolerance, hypersensitivity, or contraindication to ERT or the investigational product excipients are excluded from the study.

Participants will remain under observation in the investigational centre for at least 8 hours following infusion to minimise the risk associated with acute allergic reaction. Vital signs (pulse, blood pressure, respiration rate, and temperature) will be monitored at 15-minute intervals for the duration of the infusion. Vital signs will be monitored hourly for 6 hours following infusion and then again at 8 hours after the end of the infusion. Infusion reactions should be managed according to [Appendix 1: Suggested Management Guidelines for Infusion Reactions](#).

Myocarditis

Mild, transient myocarditis was observed in the Phase 1/2 study of FLT190 in subjects with Fabry disease. FLT190 consists of the same proprietary AAVS3 capsid however includes a different transgene which encodes α galactosidase. See the FLT201 Investigator Brochure for further details.

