## **4. General Statistical Considerations**

All study data collected will be presented in data listings, and all relevant data will be tabulated and summarized by study part, dose cohort, and overall, unless stated otherwise.

Continuous data will be described using descriptive statistics (i.e., n, mean, standard deviation, median, minimum, and maximum). Categorical data will be described using the count and percentage in each category. For the summary statistics of all numerical variables unless otherwise specified, minimum and maximum will be displayed to the same level of precision as reported. Mean and median will be displayed to one level of precision greater than the data collected. Standard deviation, standard error, and confidence intervals will be displayed to two levels of precision greater than the data collected.

Missing data will not be imputed. All analyses will be based on observed cases for the safety population unless specified otherwise.

Clinical laboratory and PK results that are below the lower limit of quantification (BLQ/LOQ), below the limit of detection (LOD), above the upper limit of quantification (ULOQ) or missing will be displayed as such in the data listings.

To calculate descriptive statistics and PK parameters, all BLQ, LOQ and LOD results will be treated as half of the BLQ/LOQ/LOD values whereas all ULOQ values will be treated as the ULOQ values as applicable.

The end of the study will be defined as the last visit by the last participant. All participants will be followed up for at least 5 years in a separate long-term follow-up study.

Unless specified otherwise, baseline will be defined as the last non-missing measurement prior to the infusion of IMP.

Change from baseline is defined as: post-baseline value – baseline value.

Study Day 1 is the calendar day of the IMP infusion. Subsequent study days are calculated as the date of assessment/event – date of infusion + 1. Pre-infusion study days are calculated as date of assessment/event – date of infusion. There is no Study Day 0.

All data are summarized based on the visit name collected on the eCRF page.

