#### 13. AAVS3 Immune Response

Immune response to the AAVS3 capsid, measured as change from baseline to each assessment point in total AAVS3 antibody titer and total AAVS3 antibody assessments (screening cut point,

screening response, specificity, titer) will be summarized (the number of participants with non-missing data, median, min, max, geometric mean, cv% (geometric coefficient variation)) by study part, dose cohort, and overall.

In addition, screening neutralizing antibody titers will be summarized for screening and pre-infusion (Day -1) visits by study part, dose cohort, and overall.

AAVS3 immune response data will be presented in a listing.

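### SAP Sections 12 and 13 ask for a geometric mean and geometric CV of a titre difference, which fail whenever a titre is unchanged or falls

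*SAP*

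**What the plan says.** SAP Section 4 sets the definition for the whole plan: "Change from baseline is defined as: post-baseline value – baseline value". It makes no exception for titres.

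SAP Section 12 takes the immune response to the transgene product as "measured as change from baseline to each assessment point in total anti-GCaSe antibody titer and neutralizing antibody titer", and says that this "will be summarized (the number of participants with non-missing data, median, min, max, geometric mean, geometric coefficient variation"). A separate sentence adds the titre itself and assay results: "Summary table will also include total and neutralizing titer assessments (screening cut point, screening response, specificity, titer), where applicable". No statistics are named for those additions.

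SAP Section 13 treats the capsid response in parallel, "measured as change from baseline to each assessment point in total AAVS3 antibody titer and total AAVS3 antibody assessments", with the same list of statistics.

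Protocol Section 7 (Table 3) and Section 15.4 make change from baseline in total and neutralising anti-GCase titre a secondary endpoint, with no mention of a ratio or log scale. On how often such antibodies should appear, Protocol Section 6.5.3.1, under its heading on anti-GCase neutralising antibodies, says that "the risk of developing antibodies, with subsequent loss of efficacy from rescue ERT, is thought to be very low". Section 6.5.3.4 repeats this for neutralising antibodies.

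**The concern.** Geometric statistics work on logarithms and need every value to be above zero. A difference from baseline need not be: it is zero for anyone whose titre does not move and negative for anyone whose titre falls. The statistic named for this secondary endpoint therefore does not fit the quantity it is applied to.

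For neutralising anti-GCase antibody, zero is the expected value, because a participant negative before and after dosing has no change. For total antibody the documents give no expected rate. Part 1 participants, however, must have started ERT or SRT at least 2 years before dosing (Protocol Section 9.1, criterion 6), so some may enter with a positive titre that can fall.

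At stake is a secondary-endpoint table that cannot be produced as specified. The SAP does not say what to do when a change is zero or negative, so the result would depend on an unrecorded programming choice.

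**Working it through.** The plan states no figure to reproduce. The check is one of definition, followed by an illustration.

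**Formulas.** Geometric mean = exp(mean of ln x). Geometric CV = 100 × √(exp(variance of ln x) − 1). Both need x > 0. If x contains a zero but no negative, the product form gives a geometric mean of 0; the geometric CV remains undefined because ln 0 does not exist. If x contains a negative, both are undefined.

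**Search for a rescuing rule.**
- The SAP Section 4 half-limit rule is written for clinical laboratory and PK results. Even if applied to titres, a participant below the limit at both visits still has a change of exactly 0.
- SAP Section 10.1 sets negative values to 0, but only for baseline-adjusted GCase activity. Applied to titres, it would still leave zeros.
- SAP Sections 12 and 13 give no ratio, log transformation or zero/negative rule.

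**Illustration (invented titres; a negative result is set to 5, half of an assumed limit of 10).**

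| Participant | Baseline | Post | Difference | Ratio |
|---|---|---|---|---|
| A | 5 | 5 | 0 | 1 |
| B | 5 | 80 | 75 | 16 |
| C | 40 | 20 | −20 | 0.5 |

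- Differences 0, 75, −20: geometric mean and geometric CV are both undefined.
- Ratios 1, 16, 0.5: geometric mean = (1 × 16 × 0.5)^(1/3) = 8^(1/3) = 2.0; geometric CV = 528%.
- Post-dose titres 5, 80, 20: geometric mean = 8000^(1/3) = 20; geometric CV = 242%.
- If all three titres are unchanged, the differences give a geometric mean of 0 and no geometric CV. The ratios give 1 and 0%.

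**How often it would happen.** Let q be the chance that a participant's change is zero or negative at a given visit. The documents give no value, so q is an assumption, shown over a range. The chance of at least one such change among n participants is 1 − (1 − q)^n.

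| q (assumed) | n = 2 | n = 3 | n = 12 |
|---|---|---|---|
| 0.1 | 0.19 | 0.27 | 0.72 |
| 0.3 | 0.51 | 0.66 | 0.99 |
| 0.5 | 0.75 | 0.875 | about 1.00 |
| 0.9 | 0.99 | 0.999 | about 1.00 |

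The first two sizes are those planned for Part 1 cohorts (Protocol Section 8.1); 12 is the approximate Part 1 total.

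**The case against.** The best defence is that little depends on these two statistics. All analysis is descriptive (SAP Section 4.2). The same table gives n, median, minimum and maximum, all valid for differences, and the data are listed. With 2 or 3 participants per cohort, those figures show nearly everything. All of this stands, and it limits the harm without making the specified statistics computable.

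One could also say that the geometric statistics were meant for the titre itself. In Section 13 that has some force, since the list of statistics follows both the change and the assay results, titre included. In Section 12 it has less: the list is attached to the change, and the titre comes in a later sentence without statistics. Replacing the mean and SD that Section 4 makes standard does suggest that log-scale reporting was intended, but the text does not say so.

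Section 13 is also less exposed in practice. Protocol Section 6.5.3.1 expects AAV dosing to stimulate neutralising antibody against the serotype, patients positive for AAVS3 neutralising antibody are excluded, and the endpoint is exploratory. Most changes there should be positive.

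A reader might infer more than the documents support:
- **That safety decisions are affected.** The temporary-halt rule (Protocol Section 13.6) and the important-medical-event definition (Section 14.3.8) act on an individual's positive result together with other individual findings. Neither uses a cohort geometric mean.
- **That responders' titres will be reported as the cohort's result.** This needs zeros to be dropped silently, and the SAP nowhere says they will be.
- **That most changes in total antibody will be zero.** The low-risk statement belongs to the discussion of neutralising antibody; no rate is given for total titre.

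**Conclusion.** The specification is wrong as written, chiefly in SAP Section 12 and with less practical effect in Section 13. If any change is zero, the geometric mean is 0 and the geometric CV undefined; if any change is negative, both are undefined. This follows from the SAP's own definition of change and does not depend on any assumed antibody rate.

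The frequencies do depend on an assumed q and on participants being independent. Over q from 0.1 to 0.9, the chance of failure at a visit runs from 19% to 99% for a cohort of 2 and from 27% to 99.9% for a cohort of 3. For neutralising antibody, the protocol's own expectation points to the upper end.

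The consequence is an unusable pair of statistics for a secondary endpoint. It does not put participant safety or the trial's conclusions at risk.

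**What to change.** In SAP Sections 12 and 13:

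1. Report geometric mean and geometric CV for the titre at each visit and for the ratio to baseline (post divided by baseline, analysed on the log scale).
2. State the value assigned to negative or below-limit titres, for example half the lowest reportable titre. Extend the Section 4 rule to titres explicitly, since it now covers only clinical laboratory and PK results.
3. Keep n, median, minimum and maximum, and no geometric statistics, for the arithmetic change. The protocol endpoint is change from baseline, so the difference should stay in the table.

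Counts of newly positive participants could be added but are not needed to correct the error.

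The cost is two SAP paragraphs, the explicit extension of the half-limit rule, and the table shells. The downside is that the geometric mean ratio depends on the value assigned to negative titres. In the illustration, assigning 10 instead of 5 changes the ratios to 1, 8 and 0.5, and the geometric mean from 2.0 to 4^(1/3) = 1.6. The assigned value should therefore be fixed in advance and printed with the table.

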#### 13. AAVS3 Immune Response

Immune response to the AAVS3 capsid, measured as change from baseline to each assessment point in total AAVS3 antibody titer and total AAVS3 antibody assessments (screening cut point,

screening response, specificity, titer) will be summarized (the number of participants with non-missing data, median, min, max, geometric mean, cv% (geometric coefficient variation)) by study part, dose cohort, and overall.

In addition, screening neutralizing antibody titers will be summarized for screening and pre-infusion (Day -1) visits by study part, dose cohort, and overall.

AAVS3 immune response data will be presented in a listing.

#### **14. Changes in the Planned Analysis**

1. Section 8.4: Analysis of exploratory endpoint Gaucher disease activity biomarkers (CCL18) is omitted from this SAP as data is not collected.
2. Section 9.2.3: Analysis of safety endpoint, clinical laboratory evaluations urinalysis is omitted from this SAP as research urine samples are not available for analysis.
3. Section 9.1.8: Adverse Events Leading to Study Discontinuation is omitted from this SAP as data is not collected.
4. In the study protocol, an interim analysis is planned but will not be performed.

